#### **8.2.4.7. Concomitant Medications**

All concomitant medication(s) as well as non-drug treatment(s) will be provided in the listings.

#### **8.2.4.8. Treatment Duration**

Duration of treatment will be summarized and split by age category and IV treatment vs. oral treatment as well as total duration. Additionally for subjects whose blood culture became negative during the course of the study, treatment duration will be summarized for the number of days of treatment until the last positive blood culture and the numbers of days of treatment from then until EOT. The number of days of treatment for subjects whose blood cultures remained positive up until EOT will be summarized.

All dosing information will be listed.

#### **8.2.4.9. Physical Examination and Vital Signs**

All physical examination and vital sign data will be provided in the listings.

#### **8.2.4.10. Fundoscopic Examinations**

The fundoscopic examination will be summarized at baseline by age category for each eye for all subjects. The number and percentage of subjects who have normal/abnormal or present/absent results will be presented. For subjects who have subsequent fundoscopic examinations, the numbers of subjects whose fundus has changed, split by whether they results were normal/abnormal or present/absent at Screening, will be presented.

The results of the fundus examination will be listed together for each visit for each subject.

#### **8.2.4.11. Use of Other Anti-Fungal Therapy**

Use of other anti-fungal therapy between EOT and Week 6 FU visit will be tabulated. Use of antifungal therapy within 30 days prior to Screening visit will also be tabulated.

#### **8.2.4.12. Screening and Other Special Purpose Data**

The intravenous catheter details will be listed.

Microbiology and histopathology results will be listed.

Signs and symptoms of ICC will be assessed at Screening, Day 10, EOIVT, EOT, Week 2 FU visit, and Week 6 FU visit and listed.

All Electrocardiogram data will be listed.

Urine or serum pregnancy testing will be performed in all females of child-bearing potential at Screening, EOT (defined as the end of IV anidulafungin if subject is not switched to oral fluconazole, or the end of the oral fluconazole if subject is switched from IV anidulafungin to oral fluconazole) and follow-up visit.

**8.2.5. Summary of Efficacy Analyses**

Endpoint	Analysis Set	Statistical Method	Model/ Covariates/ Strata	Missing Data	Interpretation
Rate of global response at EOIVT	MITT	Descriptive only	Age categories	Failure	Secondary Analysis
Rate of global response at EOIVT	MITT	Descriptive only	Age categories	Missing and indeterminate excluded	Sensitivity
Rate of global response at EOIVT	MITT	Descriptive only	Candida species	Failure	Secondary Analysis
Rate of global response at EOIVT	MITT	Descriptive only	Site of infection	Failure	Secondary Analysis
Rate of global response at EOT	MITT	Descriptive only	Age categories	Failure	Secondary Analysis
Rate of global response at EOT	MITT	Descriptive only	Candida species	Failure	Secondary Analysis
Rate of global response at EOT	MITT	Descriptive only	Site of infection	Failure	Secondary Analysis
Rate of global response at Week 2 FU	MITT	Descriptive only	Age categories	Failure	Secondary Analysis
Rate of global response at Week 2 FU	MITT	Descriptive only	Candida species	Failure	Secondary Analysis
Rate of global response at Week 2 FU	MITT	Descriptive only	Site of infection	Failure	Secondary Analysis
Rate of global response at Week 6 FU	MITT	Descriptive only	Age categories	Failure	Secondary Analysis
Rate of global response at Week 6 FU	MITT	Descriptive only	Candida species	Failure	Secondary Analysis
Rate of global response at Week 2 FU	MITT	Descriptive only	Site of infection	Failure	Secondary Analysis
Rate of relapse at Week 2 FU	MITT	Descriptive only	Age categories	Not Applicable	Secondary Analysis
Rate of relapse at Week 2 FU	MITT	Descriptive only	Candida species	Not Applicable	Secondary Analysis

Rate of relapse at Week 6 FU	MITT	Descriptive only	Age categories	Not Applicable	Secondary Analysis
Rate of relapse at Week 6 FU	MITT	Descriptive only	Candida species	Not Applicable	Secondary Analysis
Rate of new infection at Week 2 FU	MITT	Descriptive only	Age categories	Not Applicable	Secondary Analysis
Rate of new infection at Week 2 FU	MITT	Descriptive only	Candida species	Not Applicable	Secondary Analysis
Rate of new infection at Week 6 FU	MITT	Descriptive only	Age categories	Not Applicable	Secondary Analysis
Rate of new infection at Week 6 FU	MITT	Descriptive only	Candida species	Not Applicable	Secondary Analysis
All-cause mortality rate at EOIVT	MITT	Descriptive only	Age categories	Death	Secondary Analysis
All-cause mortality rate at EOIVT	MITT	Descriptive only	Candida species	Death	Secondary Analysis
All-cause mortality rate at EOT	MITT	Descriptive only	Age categories	Death	Secondary Analysis
All-cause mortality rate at EOT	MITT	Descriptive only	Candida species	Death	Secondary Analysis
All-cause mortality rate at Week 2 FU	MITT	Descriptive only	Age categories	Death	Secondary Analysis
All-cause mortality rate at Week 2 FU	MITT	Descriptive only	Candida species	Death	Secondary Analysis
All-cause mortality rate at Week 6 FU	MITT	Descriptive only	Age categories	Death	Secondary Analysis
All-cause mortality rate at Week 6 FU	MITT	Descriptive only	Candida species	Death	Secondary Analysis
Time to death (all cause mortality)	MITT	Kaplan-Meier	Age categories	Censored	Secondary Analysis

## 10. APPENDICES

### Appendix 1. DATA DERIVATION DETAILS

#### Appendix 1.1. Definition and Use of Visit Windows in Reporting

In order to capture all available data, and allocate each actual (non-missing) assessment to its closest scheduled assessment time, visit windows will be constructed around each scheduled assessment time. The actual assessment time will be calculated based on the subject's date of first dose and the subsequent assessment day. Visit windows will be determined as follows:

If two (or more) scheduled assessments occur in one window, the visit nearest to the scheduled (target) day for the window will be used, with the other(s) excluded from the analysis. If two assessments are equi-distant from the scheduled day (but either side), the assessment performed at the later time should be used. This procedure will be performed separately for each variable.

Day of Assessment	Time Point	Target Day	Definition (Day Window)
Day 1	Screening/Baseline	1	Day 1
Day 3	Day 3	3	Day 2-Day 4
Day 7	Day 7	7	Day 6 – Day 8
Day 10	Day 10	10	Day 9 – Day 11
EOIVT	EOIVT	1-35	EOIVT to EOIVT + 2 days
EOT	EOT	24-49	EOT + 2 days
2 week FU	Week 2 FU	38-63	EOT + 12 days to EOT + 20 days
6 week FU	Week 6 FU	64-77	EOT + 35 days to EOT + 49 days

Screening/Baseline will be defined as the latest evaluation performed prior to the start of therapy.

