4. Subjects undergoing treatment in the outpatient setting may have less frequent assessments, but not less than once every 7 days. Close monitoring of subjects in the outpatient setting is required.
5. A urine or serum pregnancy test will be performed at screening (prior to treatment initiation), at the end of therapy or at the end of IV therapy, whichever is later, and at the 6-week follow-up visit. Additional testing may also be performed as per request of the IRB/EC or as required by local regulations.
6. Fundoscopic exams should be performed with pupils dilated if possible. In addition, when required by the protocol, the exam should be performed by an ophthalmologist unless it is not possible for practical reasons, in which case it may be performed by the principal investigator or subinvestigator.
7. If it is not possible to perform a baseline fundoscopic examination prior to the first dose of study drug, it may be performed up to 48 hours after the first dose. Under extenuating circumstances, if the fundoscopic examination cannot be performed prior to first dose or within 48 hours, every effort should be made to perform the examination as soon as possible thereafter. Please note, if the baseline fundoscopic examination is positive for findings consistent with *Candida* endophthalmitis, then a repeat fundoscopic examination is required at the end of treatment and at the 2- and 6-week follow-up visits. Additional fundoscopic assessments, other than those required by the protocol, should also be performed as clinically indicated and according to local practice standards. In the event additional fundoscopic examinations are performed, the results should be recorded on the case report form.
8. To be completed only if the baseline fundoscopic examination was abnormal.
9. Blood cultures will be obtained on Day 1, prior to the administration of study drug, for all subjects. If a positive culture is returned, repeat cultures are required at least every 3 days until 2 consecutive cultures separated by 24 hours or more are confirmed to be negative. For subjects who are prematurely discontinued from treatment for any reason, a blood sample for culture should be obtained only if it is clinically indicated. For subjects without microbiologically confirmed ICC, further cultures will be drawn at the discretion of the investigator. Pathogen isolated will be documented

in all cases.

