### 6.3. End of IV Anidulafungin Therapy

The following assessments will be performed on the last day (or within 24 hours of the last day) of IV anidulafungin treatment:

- Targeted physical examination (including vital signs);
- Assess signs and symptoms of *Candida* infection;
- Fundoscopic examination, only if the baseline fundoscopic examination was abnormal;
- Blood cultures (for subjects with microbiologically confirmed ICC);
- Specimen culture (from other normally sterile sites as clinically indicated);
- CBC with differential (same as in screening);
- Serum chemistry (same as in screening);
- Echocardiogram, either transesophageal (preferred) or transthoracic (to be performed only in subjects with *Candida* endocarditis) (**not applicable to Korean and Portuguese investigator sites**);
- **\*\* Please Note \*\*** To be performed at the End of Treatment with IV anidulafungin in subjects who are not switched to oral fluconazole. In subjects who are switched to oral fluconazole, echocardiogram should be deferred to the End of Oral Therapy visit.
- Magnetic Resonance Imaging (MRI) study (to be performed only in subjects with *Candida* osteomyelitis) (**not applicable to Korean and Portuguese investigator sites**);
- **\*\* Please Note \*\*** To be performed at the End of Treatment with IV anidulafungin in subjects who are not switched to oral fluconazole. In subjects who are switched to oral fluconazole, echocardiogram should be deferred to the End of Oral Therapy visit.
- Evaluation of clinical and microbiologic response (See [Section 7.4](#)) (to be performed only in subjects with microbiologically confirmed ICC);
- Urine or serum pregnancy test (for females of childbearing potential) to be done at the End of Treatment period in subjects who are not switched to oral therapy.
- Record adverse events and concomitant medications.

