### **6.2.4. Fundoscopic Examination**

The fundoscopic examination assessment results are reported as normal/abnormal or present/absent at Screening for each eye and at EOIVT, EOT, Week 2 FU visit, and Week 6 FU visit if the Screening fundoscopic examination is positive for endophthalmitis. The Screening visit data will be summarized for all subjects.

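### The SAP accepts only a pre-therapy evaluation as baseline, so a child whose baseline fundoscopy was done after the first dose, as the protocol allows, has no baseline eye result in the planned summaries

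*SAP*

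**What the plan says.** **SAP.** Appendix 1.1 closes its visit-window table with a rule for all variables: "Screening/Baseline will be defined as the latest evaluation performed prior to the start of therapy". Windows run from dosing: "The actual assessment time will be calculated based on the subject's date of first dose and the subsequent assessment day". The baseline window is Day 1, followed by Days 2-4 (Day 3), Days 6-8 (Day 7) and Days 9-11 (Day 10). Fundoscopy has no exception there or in its own sections.

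Section 8.2.4.10 says: "The fundoscopic examination will be summarized at baseline by age category for each eye for all subjects". For children examined again, it counts those whose fundus changed, split by the Screening result, and it lists all results. Section 6.2.4 plans a summary of the Screening visit for all subjects and expects later results "if the Screening fundoscopic examination is positive for endophthalmitis". Section 8.2.1 includes visual tests among the primary safety parameters.

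**Protocol.** On delay, footnote 7 of the Schedule of Activities says: "it may be performed up to 48 hours after the first dose". If that too is missed under extenuating circumstances, "every effort should be made to perform the examination as soon as possible thereafter", with no outer limit. Sections 6.1 and 7.6 give the same allowance. The result decides who is examined again; section 6.3 lists "Fundoscopic examination, only if the baseline fundoscopic examination was abnormal", and footnote 8 and sections 6.4 to 6.6 agree.

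**The concern.** The protocol foresees late eye examinations and still calls them baseline. The SAP definition cannot accept any of them. Delay is easy to foresee: screening and Day 1 may be the same day (protocol 6.1), treatment may start before culture results are known (7.8.4), and an ophthalmologist should examine, with pupils dilated if possible (7.6).

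At stake is whether the SAP can produce its own fundoscopy tables. A baseline table described as covering all subjects would omit late-examined children. A change table split by Screening result would have nowhere to put them. Repeat examinations are required mainly after an abnormal first result, so the affected change data come from children who had an eye finding.

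**Working it through.** The plan gives no figure to reproduce. The check applies the SAP rule and windows to each timing the protocol permits, counting the first dose as Day 1.

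**Step 1: permitted timing.** Forty-eight hours is two days, and 1 + 2 = 3, so an examination within the limit falls on Day 1 after the dose, Day 2 or Day 3. One done later under extenuating circumstances can fall on Day 3 or any later day.

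**Step 2: map each case.**

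| First fundoscopy | Before therapy? | SAP day window | Baseline under Appendix 1.1? |
|---|---|---|---|
| Before the first dose | Yes | Screening/Baseline | Yes |
| Day 1, after the dose | No | Day 1 | No |
| Days 2-3 | No | Day 3 (Days 2-4) | No |
| Day 4 | No | Day 3 (Days 2-4) | No |
| Day 5 | No | No fixed-day window | No |
| Days 6-8 | No | Day 7 | No |
| Days 9-11 | No | Day 10 | No |

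No fundoscopy is scheduled on Day 3, 7 or 10, so those windows correspond to no planned eye table. No examination done under the allowance can be baseline.

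**Step 3: carry this into SAP 8.2.4.10.**

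- *Late and normal:* the child has no entry in the baseline table. Routine repeats are not required, so normally no change data are at stake.
- *Late and abnormal:* the child has no baseline entry, and the repeats at the end of IV therapy, the end of oral therapy and follow-up have no Screening category to be split by. Both examinations are still listed.

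**Step 4: size.** Among late-examined children the baseline entry is always lost. Neither document gives the number or proportion examined late, so no study-level count can be derived. The 60 evaluable subjects in protocol 9.4 are not the right denominator, because they are *Candida*-confirmed children and these tables use the safety set (SAP 8.2.4).

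**The case against.** The best defence is that the SAP intends the first examination whatever its timing. Appendix 1.1 aims to use all available data and assign each assessment to its nearest scheduled time. For fundoscopy, the nearest scheduled time to a Day 2-4 examination is normally Screening. The Day 1 window cannot be mechanical either, since screening may occur up to two days before dosing (protocol 6.1). Footnote 7 is attached to the Screening cell, SAP 6.2.4 speaks of the Screening visit, and SAP Appendix 2 titles its tables *First Fundoscopy*.

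This makes the intent plausible but does not override the rule. The baseline sentence is explicit about preceding therapy. The instruction to work variable by variable concerns the choice between assessments in one window, not the definition of baseline. Appendix 2 is a list of titles for the interim analysis of the two older cohorts. Two programmers could fairly produce different tables.

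Three stronger readings are tempting and not supported:

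- *Repeats done for abnormalities other than endophthalmitis go unreported.* SAP 8.2.4.10 covers any subsequent examination and lists all results. SAP 6.2.4 is narrower, but the protocol itself uses both triggers: endophthalmitis in footnote 7 and 7.6, any abnormality in footnote 8 and 6.3 to 6.6.
- *The sickest children, or a sizeable share, are lost.* Nothing in either document links delay to severity or indicates how often it happens.
- *The primary safety conclusion is compromised.* SAP 8.2.1 names visual tests, but protocol 9.1 does not name fundoscopy, and SAP 4.1 and 4.2 rule out hypothesis tests.

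**Conclusion.** The conflict is real and modest in effect. Applied as written, SAP Appendix 1.1 denies a baseline eye result to every child first examined after dosing, although SAP 8.2.4.10 promises one for all subjects. Any later change in such a child has no Screening category.

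This rests on two conditions: that the SAP sentence is programmed literally, and that at least one child uses the protocol's allowance. The number affected is unknown. The damage is limited to a descriptive safety summary. Individual results remain in the listings, and neither efficacy nor sample size is touched. It still merits correction, because a stated rule gives the wrong table and an exception for one variable cures it.

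The difference between the abnormal and endophthalmitis triggers is a separate matter of wording, with no clear loss of data.

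**What to change.** In SAP Appendix 1.1 and 8.2.4.10, add:

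*For fundoscopy, baseline is the latest examination before the first dose; if there is none, it is the first examination after the first dose within the 48 hours allowed by protocol 7.6. First examinations later than 48 hours are flagged and tabulated separately, and one done at or after the EOIVT visit is not used as baseline. Counts before, within 48 hours after, and later than 48 hours after the first dose are shown.*

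This keeps the ordinary rule wherever a pre-dose examination exists. The cut-offs stop an end-of-therapy examination from serving as its own reference.

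The cost is one derivation rule and a few table rows. The downside is that some baseline examinations will be post-dose, which the counts disclose. The rule needs examination times. If only dates are recorded, the SAP should say how a Day 1 examination is classed and apply the 48-hour limit by study day.

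Separately, align SAP 6.2.4 with 8.2.4.10 so that every repeat fundoscopy performed is reported, whatever prompted it. The protocol's two statements of when a repeat is required also need to be reconciled; which should apply is for the protocol's authors.

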**Appendix 2. Tables, Listings and Figures for Interim Analysis**

Tables
Subject Evaluation Groups
Discontinuations from study
Discontinuations from Treatment
Demographic Characteristics - Safety Population
Demographic Characteristics - MITT Population
Medical History - Safety Population
Medical History - MITT Population
Anti-infective Stratification (Site of Infection) - MITT Population
Candidemia Risk Factors - MITT Population
Summary of Baseline Candida Species - MITT Population
Anti-infective Stratification Categorization
Analysis of Global Response at EOIVT - MITT Population
Analysis of Global Response at EOIVT - MITT Population (Sensitivity Analysis - Excluding Indeterminate and Missing data)
Analysis of Global Response at EOT - MITT Population
Analysis of Global Response at EOT - MITT Population (Sensitivity Analysis - Excluding Indeterminate and Missing data)
Analysis of Global Response at 2 week follow-up - MITT Population
Analysis of Global Response at 2 week follow-up - MITT Population (Sensitivity Analysis - Excluding Indeterminate and Missing data)
Analysis of Global Response at 6 week follow-up - MITT Population
Analysis of Global Response at 6 week follow-up - MITT Population (Sensitivity Analysis - Excluding Indeterminate and Missing data)
Analysis of Clinical Cure and Microbiologic Success at EOIVT - MITT Population
Analysis of Clinical Cure and Microbiologic Success at EOT - MITT Population
Analysis of Clinical Cure and Microbiologic Success at 2 Week Follow-Up Visit. - MITT Population
Analysis of Clinical Cure and Microbiologic Success at 6 Week Follow-Up Visit. - MITT Population
Summary of Global Response - MITT Population
Summary of Clinical Response - MITT Population
Summary of Microbiological Response - MITT Population
Analysis of Rate of Relapse at 2 week follow-up - MITT Population
Analysis of Rate of Relapse at 6 week follow-up - MITT Population
Analysis of Rate of New Infection at 2 week follow-up - MITT Population
Analysis of Rate of New Infection at 6 week follow-up - MITT Population
Summary of Global Response for Site of Infection by Age Group - MITT Population
Summary of Clinical Response for Site of Infection by Age Group - MITT Population
Summary of Microbiological Response for Site of Infection by Age Group - MITT Population
Summary of Global Response by Candida Species by Age Group - MITT Population
Summary of Clinical Response by Candida species by Age Group - MITT Population

Summary of Microbiological Response by Candida species by Age Group- MITT Population
Summary of Global Response According to Neutrophil Status at Baseline (ANC $\leq$ 500 and $>$ 500) - MITT Population
Summary of All Cause Mortality - Safety Population
Summary of All Cause Mortality - MITT Population
Analysis of time to death (All Causality) - Safety population
Analysis of time to death (All Causality) - MITT population
Discontinuations Due to Adverse Events - Safety Population
Temporary Discontinuations or Dose Reductions Due to Adverse Events
Treatment Emergent Adverse Events (All Causalities) - Safety Population
Treatment Emergent Adverse Events by System Organ Class (All Causalities) - Safety Population
Summary of Treatment-Emergent Risk Events (All Causalities) - Safety Population
Treatment Emergent Adverse Events (Treatment Related) - Safety Population
Treatment Emergent Adverse Events by System Organ Class (Treatment Related - Anidulafungin and Fluconazole) – Safety Population
Treatment Emergent Adverse Events by System Organ Class (Treatment Related - Anidulafungin) – Safety Population
Treatment-Emergent Adverse Events by System Organ Class (Treatment Related - Fluconazole) – Safety Population
Incidence and Severity of Treatment Emergent Adverse Events (All Causalities) - Safety Population
Incidence and Severity of Treatment Emergent Adverse Events (Treatment Related) - Safety Population
Incidence and Severity of Treatment Emergent Adverse Events (Treatment Related - Anidulafungin) - Safety Population
Incidence and Severity of Treatment Emergent Adverse Events (Treatment Related - Fluconazole) - Safety Population
Incidence and Severity of Treatment Emergent Adverse Events - by Risk (Safety Population)
Individual Listing of Deaths
Serious Adverse Events
Basic Results Disclosure for Treatment-Emergent Non Serious Adverse Events by System Organ Class and Preferred Term (All Causalities) For events having a frequency rate greater than 2
Basic Results Disclosure for Treatment Emergent Serious Adverse Events
Incidence of Laboratory Test Abnormalities (Without Regard to Baseline Abnormality)
Incidence of Laboratory Test Abnormalities (Normal Baseline)
Incidence of Laboratory Test Abnormalities (Abnormal Baseline)
Laboratory Test Data: Median Changes from Baseline to Last Observation
Frequency Table of First Fundoscopy - Right Eye
Frequency Table of First Fundoscopy - Left Eye
Frequency Table of Fundoscopy Changes - Right Eye

Frequency Table of Fundoscopy Changes - Left Eye
Duration of Treatment - Treatment Regimen - Safety Population
Duration of Treatment - Combined Treatments - Safety Population
Duration of Treatment - Treatment Regimen - MITT Population
Duration of Treatment - Combined Treatments - MITT Population
Drug Treatments Prior to Start of Study Treatment - Safety Population
Drug Treatments During Study Treatment - Safety Population
Drug Treatments During Study Treatment - MITT Population
Drug Treatments After Study Treatment - Safety Population
Drug Treatments After Study Treatment - MITT Population
Nondrug Treatment Prior to Study Treatment
Nondrug Treatment During Study Treatment
Summary of Exclusions from MITT Population
Listings
Randomization listing
Subject Evaluation Groups
Subject Discontinuations from Study
Subject Discontinuations from Treatment
Protocol Deviations
Inclusion/Exclusion from Analysis Populations
Demographic Characteristics
Primary Diagnoses and Duration
Medical History
Drug Treatments Prior to the Start of Study Treatment
Nondrug Treatments Prior to Start of Study Treatment
Administration Schedule
Antifungal Drug Treatments
Concomitant Drug Treatments
Concomitant Nondrug Treatments
Study Treatment Compliance for Outpatient Fluconazole Treatment
[PKBDFLD] [PKTERM] Concentration ([PKCNCU]) versus Time Listing - All Age Groups
Site of Infection
Response Listing
Signs and Symptoms of Invasive Candidiasis
Microbiology Data (Local data)
Microbiology Data (Vendor data)
Histopathology/Cytology data (Local data)
Candidemia Risk Factors
Candida Osteomyelitis MRI Findings
Candida Endocarditis Echocardiogram Findings - Follow-up Assessment
Candida Endocarditis Echocardiogram Findings - Full Assessment
Adverse Events
Adverse Events (Treatment Related)
Listing of Treatment-Emergent Adverse Events – By Risk - Safety Subjects

Laboratory Data
Laboratory Test Abnormalities, by Subject
Laboratory Test Abnormalities, by Test
Vitals Signs Data
Vital Signs Change from Baseline
Electrocardiogram Data (Local data)
Electrocardiogram Data (Reference Laboratory)
Physical Examination Findings at Baseline
Physical Examination: Changes from Screening
Fundoscopy and Fundoscopy Change
Medication Error Listing
Radiographic Assessment
Intravenous Catheter Details at Baseline
Deaths (Source: Project Database)
Investigator Comments
Safety Narratives- (one output per usubid)
Figures
Kaplan-Meier Plot of Time to Death - Safety Population
Kaplan-Meier Plot of Time to Death - MITT Population

